1. BACKGROUND

Adults report being involved in a resuscitation attempt as distressing.^{1–4} Research is lacking into children's experiences of providing cardiopulmonary resuscitation (CPR). CPR was added to the curriculum for secondary schools in England in 2020⁽⁵⁾ and should be taught in all UK schools from 2022.^{6–8} We found 61% of adults had received some form of CPR training. Just 13% reported training in school.⁹ One aim of introducing CPR training in schools is to increase the number of people providing CPR in an emergency. It is likely to increase the number of children who 'attempt to save a life'.

In 2020, of 31,698 out of hospital cardiac arrests (OHCA) treated by ambulance services just 8.3% patients survived to hospital discharge. CPR performed by a member of the public (bystander) improves chances of survival. Approximately 19,300 bystanders performed CPR in England in 2020 (70% of cases). The proportion who were children is unknown, but many would likely benefit from professional support.

CPR training forms part of the 'Relationships, Health and Sex Education' curriculum in English schools, with an emphasis on mental wellbeing. However, lesson plans for CPR training focus on skills-based training rather than possible psychological impacts. Health and Social Mental health is a research priority for the NIHR and the Department for Health and Social Care (DHSC). Effectively understanding distress caused to children when they provide CPR may inform changes in CPR training and subsequent support to prevent mental health problems developing. The DHSC identifies this as key in effective mental health care. With the implementation of CPR training in schools, there is an opportunity to prepare children for the experience and signpost them to sources of support.

However, evidence to inform training guidance or support policies is lacking. Exposure to traumatic events during childhood can have lifelong impacts. Children who experience the death of a parent are more likely to develop psychiatric illnesses as an adult.¹⁵ Effective support following distressing childhood events can decrease the psychological harm resulting in long-term benefits and a reduction in healthcare service use.¹⁶ When children

have received CPR training, they have fewer negative emotions towards OHCA written scenarios.¹⁷ However, adults who have been interviewed after providing bystander CPR have criticised their training as not preparing them for the situation.¹⁸

We will explore experiences of children who have performed CPR, to understand the emotional and relationship impacts it had; the support they received including health service use, and whether this was helpful. We will discuss any CPR training they received and how well they feel this prepared them. This project is focused on experiences of psychological distress and steps that can be taken towards its prevention. Child and Adolescent Mental Health Services (CAMHS) in the UK are stretched. ¹⁹ A reduction in mental health problems will also reduce the burden on wider health services. ²⁰

We conducted three scoping reviews to explore: What are the psychological impacts on child/adolescent bystanders who witness and/or participate in an OHCA? Are there effective psychological interventions for child/adolescent bystanders who witness (+/-participate) at an OHCA? Are psychological impacts of witnessing (+/- participating) at an OHCA addressed in layperson CPR training?

We found no literature regarding the experience of children who have provided CPR. Across 13 adult studies, negative psychological reactions ranged from 1.4-76% of participants. 1-4,21-29 CPR is emotionally challenging for all lay responders with some requiring formal psychological support. 1-3 One study discussed interventions for psychological support in adult bystanders, 18 reporting short-term benefits of telephone debriefing with an emergency medical dispatcher performed 2-4 days after the resuscitation attempt. Benefits included emotional relief and safety netting in case of severe reactions and a long-term improved ability to cope with their emotional reaction. Three publications highlighted the lack of discussion around the psychological impact of CPR in layperson CPR training sessions. Bystanders reported that 'courses were too superficial and lack preparation for the "unpleasantness of OHCA". 18

Exposure to distressing events in childhood can have lifelong impacts³¹ and the impact of these events can be limited using effective psychosocial treatments such as trauma-focused CBT.¹⁶ However, as 82.3% of OHCA occur in the home,¹⁰ children who perform CPR may have the combination of attempting to 'save a life' and experiencing the resulting severe illness or death of a family member. There is no research into the effect this may have.

In preparation for this project, we sought views of members of 'Sudden Cardiac Arrest UK' (SCAUK) – a support group for survivors of sudden cardiac arrest https://www.suddencardiacarrestuk.org/) on the impact that performing CPR may have on children. From 19 responses, four reported experiences of performing CPR as a child, and the associated psychological impact: 'I had PTSD as a result' and 'Unfortunately they didn't survive... I still feel the guilt'. Other responses were from parents who described the substantial impact on children who had witnessed a resuscitation attempt, with some requiring professional psychological support. Although limited, this data suggests a substantial impact on children. There are no ongoing projects with aims that overlap with this study design registered on the International Standard Randomised Controlled Trial Number registry, clinicaltrials.gov and the European Union Clinical Trials register.

2. STUDY SUMMARY

This section presents an overview of the study,

2.1.1 Overall Study Aims

- 1. What is the experience of a child who has provided CPR to someone who has an OHCA?
- 2. How does CPR training inform and prepare children for such experiences and how can these findings inform the CPR in schools training programme?

2.1.2 Overall Study Objectives

1. To explore the experiences of children concerning the resuscitation attempt and the impact on their emotional/psychological wellbeing and relationships.

- 2. To explore the support (formal and informal) received or sought by children following providing resuscitation.
- 3. To explore the impact of CPR training on the children's experience of resuscitating someone and willingness to help in a future resuscitation attempt.

2.1.3 Study design

A qualitative interview study using reflexive thematic analysis.

2.1.4 Study Methods

Sample

A purposive sample of up to 20 children and young people in England aged 11-23 who took part in an out of hospital cardiac arrest resuscitation attempt by providing chest compressions or rescue breaths or applying defibrillation pads whilst they were aged 11-18. The cardiac arrest will have happened in the UK. Where possible, participants will be purposively selected to include a diversity of participants from different age groups, socioeconomic, ethnic, cultural and religious backgrounds and geographical areas including urban and rural locations.

Data collection

We will interview the young people who took part in a resuscitation attempt at an OHCA by providing chest compressions or rescue breaths or applying defibrillation pads whilst they were aged 11-18.

Analysis

A reflexive thematic analysis of the interview data will be conducted.

The flow diagram (Figure 1) summarises the study and timeline.

[figure not shown]

Figure 1 – flow diagram study timeline

Child CPR Study Protocol KCL ethics ID: HR/DP-23/24-34646 Version:3.0

3. PLAIN ENGLISH SUMMARY

A cardiac arrest is when someone's heart stops and they collapse. People who are there at the time can improve the person's chance of survival. They can call an ambulance, start cardio-pulmonary resuscitation (CPR) and use a heart restarter. CPR is now taught to students aged 11-18 in many UK schools. This is part of the national curriculum to help increase the number of people who know how to help.

Adults are emotionally affected by helping but we don't know how children are affected. We want to find out how children experience helping with resuscitation. This will help develop training and support for children.

We will interview people who were aged 11-18 when they helped in a cardiac arrest. We want to ask them about their experience and how it affected them, their families, friends and school life. We will also ask them about their resuscitation training. To find volunteers for interviews, we will let children and their families know about the study in different ways. We will ask schools to help us, so teachers might ask children and their parents or guardians if they would like to talk to a researcher. We will post information on groups that support people and their families who have experienced a cardiac arrest and use other social media. We will ask them to contact the study team if they are interested. We will talk to schools to make sure there is good support for those who take part. If the young person is no longer at school, we will make sure they know how to get support.

Our research team contains people who have had experience of cardiac arrest, including a young person who witnessed a cardiac arrest. We also have someone who had a cardiac arrest and started a support group for others who have survived a cardiac arrest. Another team member has experience teaching, running schools, and doing research with children. These team members will give the other members of the team advice about running the study throughout. We will look at the information in the interviews to find out what

Child CPR Study Protocol

KCL ethics ID: HR/DP-23/24-34646

Version:3.0

experiences mattered to the children, how it affected them and what support helped or didn't help. We want to find out if this is like what is already known about helping children through other difficult experiences. We will look for any improvements needed and where more research is needed. This will include possible changes to CPR training.

To inform the relevant groups of our results we will write a scientific paper and a plain English summary, have an animation/video of findings and also hold an online event announcing our results.

4. RESEARCH GOVERNANCE AND ETHICAL CONSIDERATIONS

4.1 Introduction

The study will be conducted in accordance with the NHS Research Governance Framework and the principles of Good Clinical Practice (GCP). The study will comply with relevant King's College London policies and guidance. All data will be stored securely and held in accordance with the Data Protection Act (2018). Ethical approval for the study will be sought from King's College London College Research Ethics Committee. We will work with schools involved to follow their governance processes for research conduct.

The ethical issues for the study are that participants, and for participants that are aged under 16, their parents, that their autonomy is respected. To do this we intend to gain informed consent from adult participants. We will gain informed consent from the parents/those with parental responsibility for the participants under 16. We will gain verbal assent to participate from those under 16 as well. We will also make sure participants and their parents/those with parental responsibility are aware of how to withdraw from the study.

Ensuring confidentiality of the data subjects share in interviews and their contact details required for organising participation is an important consideration.

Wellbeing of the participants is an important consideration for this study. The study participants will be healthy volunteers, however the topic of cardiac arrest and recounting

Child CPR Study Protocol

KCL ethics ID: HR/DP-23/24-34646

Version:3.0

experiences of being involved in a resuscitation attempt has the potential to cause distress to participants. We will therefore ensure support is in place within the school setting for participants still at school and for adult participants we will provide information about sources of support.

The research team will have access to sources of support as the topic could also be upsetting for them.

4.2 Informed consent:

Adult participants and young people aged 16 and 17: All participants aged 16 or over will provide their own informed consent to be involved int the study. A researcher will contact them by phone, online call or by email after they have expressed interest in being involved in the study and provide them with the participant information sheet and informed consent form. The researcher will arrange a convenient time, at least 24 hours after the information has been sent to the potential participant to talk to them about the study and answer any questions. The information will likely be sent by email, but we will be able to send them by post should the potential participant request it. If this is the case the researcher will leave sufficient time for the post to arrive when arranging the follow up conversation.

If the potential participant decides to take part the researcher will ask them to sign and return the consent form. The researcher will then sign the consent form and ensure the participant has a copy and that a copy is retained for the study records. For participants no longer in school/college (i.e. aged over 18), the researcher will arrange a convenient time and place with the participant to conduct the interview. This is likely to be face to face, but an interview via the internet (e.g. Microsoft Teams) will be an option should the participant prefer. For the young person aged 16 or 17, the researcher will make arrangements, where possible, to interview the participant at school/college, although it will be possible for interviews for all young people still in the school system to have an interview elsewhere.

It will be possible for the participant and researcher to sign the consent form at the face-to-face interview, should that be more suitable for the participant.

Before the interview starts the researcher will again check that the participant is content to proceed, giving them a further chance to ask any questions.

Participants under 16: Consent will be sought from the parents/those with parental responsibility for participants under 16. All participants themselves will be given the opportunity to discuss participation and provide their verbal assent as well, which will be recorded before the interview starts.

Once parents or those with parental responsibility for the child have indicated an interest in their child taking part in the study, the researcher will provide them with an information sheet (if they need another copy) and a consent form and they will be given the opportunity to ask the study researcher questions. They will be encouraged to discuss participation with their child and if they decide they want their child to take part both they and the child will be given the opportunity to ask the researcher more questions, before the researcher asks the parent to sign the consent form. This can be done via telephone or online discussion and information can be sent to the parent by email or post. The signed consent form can be returned by email or post.

For all participants under 18 who are still attending school, whether identified by the school/college or through another route, the study team will explain to the young person and their parent that we would prefer the interview take place at the young person's school. The researcher will explain the reasons for this and seek their verbal consent to contact the school to arrange this. If they agree, the researcher will then contact the school to gain agreement for a suitable room in the school to be made available for the interview. We will also need agreement that the school will be able to provide suitable emotional and safeguarding support for the participant before we go ahead with the interview. For pupils who are not introduced to us by the school themselves, we will ask the child's parent for the

Child CPR Study Protocol

KCL ethics ID: HR/DP-23/24-34646

Version:3.0

school's contact details and, if necessary, a supporting email or phone call. The study team will then contact the school to explain what is involved and gain appropriate permissions.

Once the school has agreed a suitable time for the child, parent and school will be arranged for the interview.

If the school does not give permission for interviews to be conducted on school premises, and the young person is still in the school system, we will establish if the school would be prepared to support the child should we interview them elsewhere and, if so, how. If the school is able to provide support if needed, we will then discuss with the parent and decide a suitable location for the interview. This location may be at one of the collaborator's universities (if the child lives near enough that travel would be easy), or at the child's home with the parent's/person with parental responsibility's permission. If the interview takes place in the home, a parent must be present in the home at the time of the interview. The child will be able to choose whether they want their parent to be in the same room with them during the interview. The researcher will give the parent and the child/young person information about sources of support such as child line, the Samaritans and their GP should they want support after the interview.

During the consent process the researcher will ask the participant or their parent/person with parental responsibility (as age appropriate) for consent to contact them approximately two weeks after the interview to check on the participant's wellbeing and if necessary direct them to sources of support.

For all participants: Once the interview is organised at the school, or other venue the researcher will check at the start of the interview with all participants they understand, have any questions and whether they want to continue. Those aged 16 or over that give their verbal assent will continue and those that do not will be withdrawn from the study. Young people <16 years will be asked to verbally agree (or disagree) with assent statements read out by the researcher, and this verbal assent will be audio recorded and stored safely with

their parent's signed consent form. These assent statements will have been emailed to them in advance to give them the opportunity to discuss with their parent(s) and to contact the researcher with any questions prior to the interview. If the child doesn't not want to continue with the interview they can withdraw at this point.

4.3 Confidentiality:

All results and findings reported will be anonymised, to ensure no individuals can be identified in the study. Participant and parental information will be obtained, used and stored in compliance with the 2018 Data protection act. Further details are given in section 8.

4.4 Wellbeing and safeguarding

The study participants will be healthy volunteers, however the topic of cardiac arrest and using resuscitation techniques has the potential to cause distress to participants.

We intend to hold interviews with young people who are still in fulltime education at their school or college and therefore we will follow safeguarding procedures in line with local policy. The team will develop study specific guidance on safeguarding.

During the interview, the researcher will provide a time-out or stop the interview if the participant becomes distressed. Participants will be directed to appropriate support as per a developed protocol including school councillors, Chain of Survival UK (COSUK), GP services, CAMHS and Improving Access to Psychological Therapies. Should an urgent mental health issue arise the researcher will be able to call 999 or 111 as appropriate, involving the school, parent or adult participant themselves as appropriate.

We will work closely with the schools to ensure an adult member of staff familiar with safeguarding policies and procedures for the school is available at the time of the interviews

so the researcher conducting the interview is able to work with the school representative should any safeguarding issues be raised during the interview. This process will be the same if the child becomes distressed and needs support. Where a child is clearly upset the researcher will stop the interview and seek support from the designated school member of staff. The schools' procedures will be followed, and a record made of what happened and what action was taken and who at the school took the issue forward for the research team's records. The researcher will have appropriate checks (DBS) for working with young people and undertake safeguarding training appropriate to the age group and setting where they will be working. King's College London has safeguarding policies and support which will inform the study guidance. For adult participants we will provide information on sources of support. All participants will be able to request that the interview is stopped at any point and will not have to answer any questions they do not want to. The researcher will check in with participants at different points of the interview to see if they want to continue.

If the school does not give permission for interviews to be conducted on school premises or the parent/young person over 16 refuses to have the interview at the school, and the young person is still in the school system, we will establish if the school would be prepared to support the child should we interview them elsewhere and, if so, how. If the school is able to provide support if needed, we will then discuss with the parent and decide a suitable location for the interview. This location may be at one of the collaborator's universities (if the child lives near enough that travel would be easy), or at the child's home with the parent's/person with parental responsibility's permission. If the interview takes place in the home, a parent must be present in the home at the time of the interview. The child will be able to choose whether they want their parent to be in the same room with them during the interview. The researcher will give the parent and the child/young person information about sources of support such as child line, the Samaritans and their GP should they want support after the interview. See Section D1e(iii) for further details.

Child CPR Study Protocol

KCL ethics ID: HR/DP-23/24-34646

Version:3.0

For participants or their parent/person with parental responsibility (as age appropriate) who have provided consent, the researchers will contact them approximately two weeks after the interview to check on the participant's wellbeing and if necessary direct them to sources of support.

The researcher will ensure they have details of the local Multi-Agency Safeguarding Hub (MASH) service (or equivalent) in the area and how to make a referral in case there are any safeguarding issues that the child raises in the interview. If the researcher does have safeguarding concerns and it is safe for them to do so, they will inform the parent of their concerns and that they are contacting the MASH. As soon as feasible, the researcher will inform the CI or another member of the study team about what has happened. Once the researcher returns to work, they will record their concerns and actions in the study records and any subsequent information that arises. The researcher will be able to talk to the CI and, if they prefer, to the staff support services at the University about the impact of the incident on them.

In the unlikely event that an adult participant raises an issue of current safeguarding concern the researcher will discuss the situation with the study leads and team who will make a decision on what action to take based on their responsibilities as researchers in this situation.

Study team support: We will develop a support structure for members of the study team. Exploring the topic and hearing about people's experiences has the potential to be distressing or concerning to the researchers and other members of the team. We will consider a buddying system, where a member of the team has an identified buddy they can talk to following data collection. The CI will be available to members of the research team to debrief after data collection, should they wish, and the King's College London has welfare support available to all members of staff should team members need or prefer such confidential support.

We will develop proportionate approaches with our research partners on how researchers will respond to sensitive disclosures made by study participants.

We will follow King's College London guidance and risk assessment templates with regards to lone working for the study team.

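### For interviews away from school, section 4.4 makes telling the parent of a safeguarding concern depend on the researcher's safety alone, with no condition for the child and no exception for a concern about that household

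*Protocol*

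**What the plan says.** Section 4.4 of the protocol describes three routes for a safeguarding concern.

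- **At school.** This is the preferred venue for participants still in education. A staff member who knows the school's safeguarding policies is to be available "so the researcher conducting the interview is able to work with the school representative should any safeguarding issues be raised during the interview". It adds: "The schools' procedures will be followed, and a record made of what happened".
- **Away from school.** If the school does not allow interviews on its premises, or the parent or older participant declines the school as venue, the interview may move to a collaborating university or the child's home, provided the school can still offer support. Sections 4.2 and 4.4 both state: "If the interview takes place in the home, a parent must be present in the home at the time of the interview". The researcher carries the details of the local MASH. Then comes the rule at issue: "If the researcher does have safeguarding concerns and it is safe for them to do so, they will inform the parent of their concerns". The same sentence adds the referral to what the parent is told: "they will inform the parent of their concerns and that they are contacting the MASH". Two steps follow: "As soon as feasible, the researcher will inform the CI or another member of the study team about what has happened", and "Once the researcher returns to work, they will record their concerns and actions in the study records".
- **Adult participants.** If an adult raises a current safeguarding concern, "the researcher will discuss the situation with the study leads and team who will make a decision on what action to take".

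Section 4.4 also promises study-specific safeguarding guidance and an agreed approach to sensitive disclosures. Neither is set out in the protocol.

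**The concern.** The rule makes informing the parent the default and attaches one test to it. That test, read plainly, asks about the person doing the informing. It does not ask what happens to the child once the parent knows. Where the concern is about someone outside the family this may do no harm. Where it is about the parent, or someone living with the child, the same default alerts the possible source of the risk.

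Such a disclosure is foreseeable. The first study objective (section 2.1.2) covers effects on wellbeing and relationships, and the plain English summary (section 3) says participants will be asked how the event affected their families. Section 4.4 itself plans for the child raising a safeguarding issue during the interview. At stake is the safety of a minor who took part in the research. The analysis is not affected.

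**Working it through.** No arithmetic applies, because the point rests on no sample size, rate or other figure. The check is to read the provisions together and see whether any of them supplies what the sentence leaves out.

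1. **Whose safety is tested?** In "If the researcher does have safeguarding concerns and it is safe for them to do so, they will inform the parent of their concerns" the only person named before the condition is the researcher. The pronouns in the condition and in the main clause both refer back to that person. The child is not mentioned in the sentence.

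2. **When is the parent told?** In "they will inform the parent of their concerns and that they are contacting the MASH" the referral is in the present continuous, so the parent hears of it before or while it is made. Nothing requires advice from the MASH or the study team beforehand.

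3. **Is anyone consulted first?** The Chief Investigator or a colleague is told afterwards: "As soon as feasible, the researcher will inform the CI or another member of the study team about what has happened". The written record comes later still: "Once the researcher returns to work, they will record their concerns and actions in the study records". For adult participants the order is reversed, because the team decides before action is taken: "the researcher will discuss the situation with the study leads and team who will make a decision on what action to take". The rule for children therefore builds in less deliberation than the rule for adults.

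4. **Where is the parent?** At a home interview a parent must be in the building. The home is one of the two named alternatives to school, and section 4.4 lets a parent's refusal of the school be the reason for using one of them.

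5. **Does any other provision add a condition for the child, or an exception?**
   - The sentences on distress, time-outs and emergency calls deal with upset and urgent mental health problems. They do not cover a concern about a parent.
   - The sources of support are handed to parent and child alike.
   - The wellbeing contact about two weeks later goes to the participant or the parent according to age and consent. For a younger child it may reach the same parent.
   - The school procedures govern the school route.
   - The study guidance and the approach to disclosures are still to be written.

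No provision shown in the protocol supplies the missing condition or the missing exception.

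6. **Which interviews are covered?** The MASH paragraph carries no label of its own. It follows the text on out-of-school venues and refers to the researcher's return to work, while school interviews have their own procedure. The point is therefore limited to interviews outside school.

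**The case against.** The strongest reply is that the condition is loosely worded and can be read generously. A researcher with the safeguarding training that section 4.4 requires might take it to mean that the parent is told only if telling is safe all round. That would cover a parent who is the source of the risk. The promised guidance and the sponsor's policies may say so outright. Section 4.4 also refers to a section numbered D1e(iii), which is not part of this protocol and cannot be weighed. And school is the preferred venue, so the rule may seldom be used.

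Part of this stands. The wording is ambiguous rather than plainly perverse, the scope is narrow, and what a trained researcher would do cannot be known from the text. It does not remove the point. The protocol did not leave the matter to later guidance: it fixed a default, and guidance written afterwards would have to depart from it. A researcher deciding alone in a family's home should not need to supply the generous reading.

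A reader might infer more than the document supports:

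- **That the school route has the same gap for concerns about staff.** Section 4.4 applies each school's own procedures there, and these are not shown. Whether they cover concerns about staff cannot be judged.
- **That the parent is told on the spot and the child is then left at home with them.** This is an inference, strongest for home interviews. The protocol says when the record is made. It does not say when the researcher leaves or what happens to the child meanwhile.
- **That the rule fails in the very case it was written for.** It covers any safeguarding issue the child raises. A concern about the parent is only one kind.

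**Conclusion.** The point holds for interviews away from school. As written, section 4.4 makes informing the parent the default on a single condition, which on its plain reading concerns the researcher. The child's safety is not a stated condition, and a concern involving the parent or a household member is not excepted. This is a stated rule that can misdirect, rather than detail left for another document.

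Its size cannot be put as a probability. The protocol gives a ceiling of 20 participants aged 11 to 23. It does not say how many will be minors, how many interviews will take place outside school, or how often such disclosures occur. Any percentage would only restate assumptions about those three quantities. The case for change rests on the possible seriousness of a single instance and the ease of preventing it. It assumes the plain grammatical reading of the condition; on a broader reading the sentence is still unclear enough to need rewording.

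**What to change.** In section 4.4, reword the condition so that the parent is informed only where doing so would not put the child or the researcher at further risk. Add an exception to the default of informing the parent where the concern involves a parent or a member of the household. Agree the order of contacts (MASH, Chief Investigator, family) with the sponsor's safeguarding lead, and make the protocol text and the promised study-specific guidance say the same thing. The school route needs no change on this account.

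The cost is one or two sentences, submitted as an amendment to the sponsor's ethics committee after the Study Management Group has considered it, as section 10.2 provides. Recruitment criteria, interview content and the thematic analysis are untouched.
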